3.13.5. Exploratory Endpoints

Unless otherwise specified, exploratory efficacy analyses will be guided by treatment policy strategy using all randomized population. Missing data will not be imputed.

 Table GPID.3.5.
 Exploratory Efficacy Endpoints and Analyses

Objectives	Endpoints	Analytical Approaches
Atrial fibrillation	 Proportion of participants with atrial fibrillation at Week 24 and at Week 52. Proportion of participants with atrial fibrillation at Week 24 and at Week 52 among those without atrial fibrillation at baseline. Proportion of participants without atrial fibrillation at Week 24 and at Week 52 among those with atrial fibrillation at baseline. 	Fisher's exact test or logistic regression analysis including treatment, stratification factors, and baseline atrial fibrillation status will be conducted.
Waist circumference	Change from baseline in waist circumference	MMRM analysis similar to the model described in Section 3.13.1.4 will be conducted.
Patient-reported health-related quality of life	Change from baseline in KCCQ: Total Symptom Score (TSS) Overall Summary Score (OSS)	MMRM analysis similar to the model described in Section 3.13.1.4 will be conducted.
Patient-reported health status	Change from baseline in EQ-5D-5L (measured at 24 weeks and 52 weeks): • Index Score, and • VAS Score.	MMRM analysis similar to the model described in Section 3.13.1.4 will be conducted.
PGIS	Proportion of participants with improvements from baseline in: PGIS – Overall PGIS – Physical Function, and PGIS – Symptom Severity.	Proportion of participants with improvements from baseline will be summarized. Shift analysis from baseline to Week 24 and to Week 52 will also be performed.
Evaluation of prespecified biomarkers	Change from baseline in: NT-proBNP cTNT	MMRM analysis similar to the model described in Section 3.13.1.4 will be conducted. The data will be log-transformed for the analysis.
Waist to height ratio	Change from baseline to Week 52 in waist to height ratio	MMRM analysis similar to the model described in Section 3.13.1.4 will be conducted.
Kidney function	eGFR slope	The slope analysis will be constructed with eGFR as a dependent variable, including treatment group, stratification factors, baseline eGFR, time (as a continuous variable) and treatment-by-time interaction as fixed effects, and including subject as a random intercept and time as a random slope

Abbreviations: cTNT = cardiac troponin T; eGFR = estimated glomerular filtration rate; EQ-5D-5L = EuroQOL 5 Dimension 5 Level scale; KCCQ = Kansas City Cardiomyopathy Questionnaire; MMRM = mixed-effects model repeated measures; NT-proBNP = N-terminal pro-B-type natriuretic peptide; PGIS = Patient Global Impression of Severity; VAS = visual analog scale.

Note: Additional exploratory analysis may be conducted.

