Study I8F-MC-GPID	Study Period I Screen ing									St	udy P	eriod l	I - Treatmen	t period						
															Unsc	heduled V	isit (UV)ª			
Visit number	1	2	3	4	5	6	7	8	9	10	11	12	EVa, EVb, EVc (13, 14, 15, 17, 18, 19, etc.)	EVd (16, 20, etc.)	UV	Dosing UV	Phone Follow- Up Dosing UV	E T	99	Comment
Weeks from randomization	-6	0	4	8	1 2	1 6	2 0	2 4	3 2	40	48	52	(+3, 6, 9, 15, 18, 21 months from Visit 12)	(+12 , 24 mon ths from Visit 12)				_	Fina 1 Visit	See footnote b
Visit interval tolerance (days)			± 3	± 3	± 3	± 3	± 3	± 3	± 7	±7	±7	±7	±15	±15				_		
Telephone Visit			3	3	3	3	3	3	X		X		X				X			See footnote c
Cardiac troponin T (cTnT)		X			X			X				X						X d		See footnote d
Calcitonin	X							X				X		X				X	X	
Cystatin C		X			X			X				X						X		See footnote d
C-reactive protein, high-sensitivity (hsCRP)		X			X			X				X						X		See footnote d
Pancreatic amylase	X	X j			X			X		X		X		X				X	X	See footnote j

Study I8F-MC-GPID	Study Period I Screen ing									St	tudy P	eriod l	I - Treatmen	t period						
															Unsc	heduled V	isit (UV)ª			
Visit number	1	2	3	4	5	6	7	8	9	10	11	12	EVa, EVb, EVc (13, 14, 15, 17, 18, 19, etc.)	EVd (16, 20, etc.)	UV	Dosing UV	Phone Follow- Up Dosing UV	E	99	Comment
Weeks from randomization	-6	0	4	8	1 2	1 6	2 0	2 4	3 2	40	48	52	(+3, 6, 9, 15, 18, 21 months from Visit 12)	(+12, 24 mon ths from Visit 12)					Fina 1 Visit	See footnote b
Visit interval			±	±	±	±	±	±	±	±7	±7	±7	±15	±15				_		
tolerance (days)			3	3	3	3	3	3	7											
Telephone Visit Lipase	X	X			X			X	X	X	X	X	X	X			X	X	X	See footnote c See footnote j
eGFR (CKD-EPI)	X	ў Х 1			X			X				X		X				X	X	The CKD-EPI equation will be used by the central lab to estimate and report eGFR. See footnote l
Urinary albumin/creatinine ratio (UACR)	X							X				X		X				X	X	

Study I8F-MC-GPID	Study Period I Screen ing									St	udy P	eriod l	I - Treatmen	t period						
															Unsc	heduled V	isit (UV)ª			
Visit number	1	2	3	4	5	6	7	8	9	10	11	12	EVa, EVb, EVc (13, 14, 15, 17, 18, 19,	EVd (16, 20, etc.)	UV	Dosing UV	Phone Follow- Up Dosing UV	E	99	Comment
Weeks from randomization	-6	0	4	8	1 2	1 6	2 0	2 4	3 2	40	48	52	etc.) (+3, 6, 9, 15, 18, 21 months from Visit 12)	(+12, 24 mon ths from Visit 12)				_	Fina 1 Visit	See footnote b
Visit interval			±	±	±	±	±	±	±	±7	±7	±7	±15	±15				_		
tolerance (days)			3	3	3	3	3	3	7											
Telephone Visit									X		X		X				X			See footnote c

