- c Telephone visits can become office visits. Site documentation will serve as the source for telephone visits. Additional, optional telephone visits may be conducted at investigator discretion. If patient requires study drug at a telephone visit, the participant will need to come to the clinic to pick up study drug in addition to telephone visit.
- d Perform at ET only if participant early terminates at or prior to Week 52.
- e Two 6MWTs conducted at screening visit.
- f See Section 10.10.1 to determine if the 6MWT needs to be repeated for Visit 2.
- g This includes glucose monitoring for participants with T2D, weekly study drug injection.
- h Perform PRO at ET only if participant early terminates at or prior to Week 52.
- i Unscheduled Visits: laboratory tests may be drawn according to investigator discretion. If only re-test labs required, site is not required to complete an unscheduled visit and associated procedures.
- Required at Visit 2 randomization if screening labs are older than 28 days for chemistry, lipid, and pancreatic lipase/amylase.
- k Collect serum pregnancy at Visit 2 only if Visit 1 serum was ≥28 days prior.
- 1 Only collect calculated eGFR with Clinical Chemistry sample if screening labs are older than 28 days.

2. Introduction

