12 patients in the placebo group, but only in 1 patient in the semaglutide group (HR 0.08; 95% CI 0.00 to 0.42)

It has been demonstrated that tirzepatide can provide significant body weight loss and improvement of lipid and glucose metabolism in patients with and without T2DM (Frias et al. 2018; Wilson et al. 2020; Jastreboff et al. 2022). It is known that the body weight reduction with GLP-1 RAs in patients without T2DM is higher than in patients with T2DM (Davies et al. 2015; Pi-Sunyer et al. 2015; Lingvay et al. 2018). If Study GPID is assumed to include 40% to 50% of patients with T2DM, the mean placebo-adjusted body weight percent reduction that tirzepatide can provide in 52 weeks in this study is estimated to be 15% to 16%. This is based on tirzepatide clinical data and the understanding of body weight loss differences between patients with and without T2DM treated with GLP-1 RAs. Thus, the predicted body weight loss with treatment with tirzepatide is close to that shown with bariatric surgery.

Tirzepatide may provide benefit to patients with HFpEF and obesity by virtue of cardiometabolic improvements (Wilson et al. 2020). Given the wide distribution of GIP receptor in the adipose tissue, GIP is thought to be actively involved in lipid and glucose metabolism. As suggested by the results of emerging data (Kosiborod et al. 2023) and the significant weight loss achieved with tirzepatide, the effect of tirzepatide on HF events in an obesity-related HFpEF population are expected to be robust. Therefore, it will be meaningful to assess the impact of tirzepatide not only on functional and symptomatic endpoints but also on the reduction in the risk of HF events in SUMMIT, thereby facilitating the holistic understanding of the clinical impact of tirzepatide treatment in patients with HFpEF and obesity.

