9.4.4. Tertiary/Exploratory Endpoint(s)

The analyses for exploratory endpoints will be described in the SAP. Statistical tests will be performed at the two-sided significance level of 0.05. There will be no multiplicity adjustment for any analysis of exploratory variables unless specified otherwise. Missing values will not be explicitly imputed unless specified otherwise.

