10.2. Appendix 2: Clinical Laboratory Tests

- Clinical laboratory testing will be performed according to the SoA (Section 1.3).
- Central and local laboratories will be used. The table below describes when the local or central laboratory will be used
- In circumstances where the sponsor approves local laboratory testing in lieu of central laboratory testing (in the table below), the local laboratory must be qualified in accordance with applicable local regulations.
- Protocol-specific requirements for inclusion or exclusion of participants are detailed in Section 5 of the protocol.
- Additional tests may be performed at any time during the study as determined necessary by the investigator or required by local regulations.
- Pregnancy testing will be performed according to the SoA.
- Investigators must document their review of the laboratory safety results. Laboratory results that will not be reported to investigative sites or other blinded personnel are noted in the table below.

Refer to Section 10.7 for recommended laboratory testing for hypersensitivity events.

Clinical Laboratory Tests	Comments
Hematology	Assayed by Lilly-designated laboratory.
Hemoglobin	
Hematocrit	
Erythrocyte count (RBCs [red blood cells])	
Mean cell volume	
Mean cell hemoglobin concentration	
Leukocytes (WBCs [white blood cells])	
Differential	
Neutrophils, segmented	
Lymphocytes	
Monocytes	
Eosinophils	
Basophils	
Platelets	
Clinical Chemistry	Assayed by Lilly-designated laboratory.
Sodium	
Potassium	
Chloride	
Bicarbonate	

Clinical Laboratory Tests	Comments
Total bilirubin	
Direct bilirubin	
Alkaline phosphatase (ALP)	
Alanine aminotransferase (ALT)	
Aspartate aminotransferase (AST)	
Gamma-glutamyl transferase (GGT)	
Blood urea nitrogen (BUN)	
Creatinine	
Creatine kinase (CK)	
Uric acid	
Total protein	
Albumin	
Calcium	
Phosphorus	
Glucose	
Lipids	
Total cholesterol	
Direct LDL-C	
HDL-C	
VLDL-C	
Triglycerides	
Pancreas (Exocrine)	Assayed by Lilly-designated laboratory.
Pancreatic amylase	
Lipase	
Special Chemistry	Assayed by Lilly-designated laboratory.
Hemoglobin A1c (HbA1c)	
Calcitonin	
Cystatin C	
N-terminal pro b-type natriuretic peptide (NT-	
proBNP)	
Cardiac troponin T (cTnT)	
C-reactive protein, high-sensitivity (hsCRP)	
Thyroid stimulating hormone	
Urine Chemistry	Assayed by Lilly-designated laboratory.
Albumin	
Creatinine	
Calculation	
eGFR (calculated by CKD-EPI equation)	Will be calculated by the Lilly-designated laboratory at all visits.

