3.14.3.13. Renal Safety

Laboratory measures related to renal safety will be analyzed as specified for laboratory measurements in Section 3.14.5.

In addition, two shift tables examining renal function will be created. A minimum-to-minimum shift table of estimated glomerular filtration rate (eGFR) estimated by the Chronic Kidney Disease Epidemiology Collaboration (CKD-EPI) equation with unit as mL/min/1.73m², using categories ($<30, \ge 30$ to $<45, \ge 45$ to $<60, \ge 60$ to <90, and ≥ 90 mL/min/1.73m²). A maximum-to-maximum shift table of urine albumin-to-creatinine ratio (UACR), using the categories UACR <30 mg/g, 30 mg/g \le UACR ≤ 300 mg/g, UACR ≥ 300 mg/g (respectively, these represent normal, microalbuminuria, and macroalbuminuria).

MMRM analyses as described in Section 3.14 for eGFR and UACR will be provided. Log-transformation will be performed for UACR.

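### The eGFR slope and the renal-safety eGFR analyses appear to rest on creatinine alone in a trial expecting 15% to 16% weight loss; cystatin C is collected to Week 52 but the SAP names it in no analysis

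*SAP*

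**What the plan says.** Kidney function is an exploratory objective with one endpoint, eGFR slope (Protocol Section 3; SAP 3.13.5, Table GPID.3.5). "The slope analysis will be constructed with eGFR as a dependent variable", with continuous time, a treatment-by-time interaction, and a random intercept and slope. Protocol 9.4.4 says of exploratory endpoints: "Statistical tests will be performed at the two-sided significance level of 0.05". There is no multiplicity adjustment.

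In renal safety (SAP 3.14.3.13), a shift table uses eGFR "estimated by the Chronic Kidney Disease Epidemiology Collaboration (CKD-EPI) equation", and "MMRM analyses as described in Section 3.14 for eGFR and UACR will be provided". SAP 3.14 runs the safety MMRM on planned visits up to 104 weeks.

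On the source of eGFR, the Schedule of Activities says: "The CKD-EPI equation will be used by the central lab to estimate and report eGFR". Its footnote for Visit 2 reads: "Only collect calculated eGFR with Clinical Chemistry sample if screening labs are older than 28 days". Protocol Appendix 2 adds: "Will be calculated by the Lilly-designated laboratory at all visits".

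On expected weight loss, Protocol 2.2 says: "the mean placebo-adjusted body weight percent reduction that tirzepatide can provide in 52 weeks in this study is estimated to be 15% to 16" percent, if 40% to 50% of participants have type 2 diabetes.

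Cystatin C is scheduled at Visits 2, 5, 8 and 12 (Weeks 0, 12, 24 and 52), and at early termination if that occurs at or before Week 52. The SAP does not mention it. The prespecified biomarkers in Table GPID.3.5 are NT-proBNP and cardiac troponin T, and the renal-safety section names only eGFR and UACR.

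**The concern.** Serum creatinine reflects muscle mass as well as filtration. That is a general physiological premise; neither document discusses it. If weight loss on tirzepatide includes muscle, creatinine can fall and eGFR can rise with true filtration unchanged, and this would happen mainly in one arm. Randomisation does not protect against it, because it arises after randomisation and through treatment. The treatment-by-time term would then mix body composition with kidney function.

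Two readings are exposed. The exploratory slope could look better than the kidneys are. The eGFR part of renal safety could also understate a real decline. The second matters because Protocol 10.5.1.12 itself warns that gastrointestinal events may cause dehydration and worsen renal function. Reduced function will be common at entry, since inclusion criterion 6 can be met by eGFR below 70. A second filtration marker is already being drawn, but no analysis is committed to it.

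**Working it through.** The plan gives no power or effect figure for eGFR slope, so there is none to reproduce. The check has three parts.

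**1. Which marker does the reported eGFR use?** No passage says outright. Three facts point the same way.
- The Visit 2 footnote ties eGFR to the Clinical Chemistry sample.
- Protocol Appendix 2 lists creatinine under Clinical Chemistry and cystatin C under Special Chemistry.
- eGFR is scheduled at Visit 1, EVd and Visit 99, where no cystatin C is drawn. At those visits it cannot use cystatin C.

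So creatinine-based is a strong inference from the schedule, not a statement in the documents.

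**2. How large could the artefact be?** Assume eGFR is proportional to creatinine to the power −k, and that creatinine falls by a fraction f through muscle loss alone. Then

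false gain = baseline eGFR × [(1 − f)^(−k) − 1].

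Both k (1.0 to 1.2) and f (0% to 8%) are assumptions. Results in mL/min/1.73 m², for k = 1.0 to k = 1.2:

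| f | baseline 45 | baseline 60 |
|---|---|---|
| 0% | 0 | 0 |
| 2% | 0.9 to 1.1 | 1.2 to 1.5 |
| 5% | 2.4 to 2.9 | 3.2 to 3.8 |
| 8% | 3.9 to 4.7 | 5.2 to 6.3 |

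Worked case: 60 × (0.92^(−1.2) − 1) = 60 × 0.105 = 6.3.

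**3. How much of it reaches each analysis?** Suppose the artefact builds linearly to Week 52 and then stays flat.
- *Slope, follow-up to about Week 52:* all of it enters the yearly slope.
- *Slope, follow-up to Week 104 (EVd):* take a least-squares line through Weeks 0, 12, 24, 52 and 104, with the artefact as a fraction of its one-year value: 0, 0.231, 0.462, 1, 1. Mean week is 38.4, Sxx = 6867.2 and Sxy = 66.46. The slope is 66.46/6867.2 × 52 = 0.50 of the yearly figure. Without Week 0 (mean week 48, Sxx = 5024, Sxy = 40.62) it is 0.42.
- *Example:* at baseline 60 and f = 5%, 3.2 to 3.8 per year becomes about 1.6 to 1.9 (× 0.50) or 1.3 to 1.6 (× 0.42).
- *MMRM:* visit is a factor, so under this pattern the Week 52 contrast carries the artefact undiluted.

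**The case against.** The strongest case against has six parts.

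- **Low stakes.** The slope is exploratory and outside the alpha-controlled family. This stands: no primary or key secondary conclusion depends on it.
- **Cystatin C may not be unused.** SAP 3.14.3.13 sends renal laboratory measures to 3.14.5, which gives descriptive summaries, shift tables with Fisher's exact test, and models for selected tests. Raw cystatin C could fall under that text. This stands, so a reader who infers that cystatin C will be ignored goes beyond the documents. But nothing there commits to an eGFR calculated from cystatin C, or to a slope of it. The note to Table GPID.3.5 allowing further exploratory analysis also specifies none.
- **The size is assumed.** This stands. The assumed range includes zero. A reader might infer that the artefact matches or exceeds a typical yearly decline. The documents give no yearly decline, and against an assumed 1 to 4 mL/min/1.73 m² several entries in the table fall short.
- **Slopes past Week 52 dilute it.** This stands, by about half in the pattern above. It does not apply to participants with about one year of data, or to the Week 52 MMRM contrast.
- **Cystatin C is no clean referee.** It may itself shift with adiposity. If it falls with fat loss, its eGFR also rises. A rule that a kidney claim needs both markers to agree in direction could then confirm a false benefit. This stands, and such a rule should not be adopted.
- **Renal safety has other evidence.** UACR, acute renal failure and chronic kidney disease searches, and dehydration events are all analysed. This stands: only the eGFR component is exposed.

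**Conclusion.** The gap is real but modest. The eGFR in the exploratory slope, and in the renal-safety shift table and MMRM, is creatinine-based on the evidence of the schedule and laboratory list. With 15% to 16% placebo-adjusted weight loss expected, any muscle loss on tirzepatide could bias the contrast upward. The SAP prespecifies no cystatin C eGFR that would let a reader judge this.

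Under the assumed 0% to 8% creatinine fall and exponent of 1.0 to 1.2, the bias is about 0 to 6 mL/min/1.73 m² at eGFR 60 by one year, and about 0.4 to 0.5 of that per year in slopes running to Week 104 if it plateaus after Week 52. The documents do not show that the bias will occur, or that any observed kidney benefit would be false. They show only that the planned analyses could not tell the two apart.

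**What to change.** 1. In SAP Table GPID.3.5 and Section 3.14.3.13, state that the reported eGFR is the creatinine-based CKD-EPI value, if that is what the sponsor intends.
2. Prespecify sensitivity analyses that repeat the slope model and the renal-safety MMRM through Week 52 with two further outcomes: CKD-EPI eGFR from creatinine plus cystatin C, and from cystatin C alone. Show them beside the creatinine eGFR restricted to the same visits (Weeks 0, 12, 24 and 52, with early termination up to Week 52 where the model uses it).
3. State a rule for baseline pairing. When Visit 2 chemistry is not drawn because screening results are no older than 28 days, say whether Visit 1 creatinine is paired with Visit 2 cystatin C. The gap is then at most 28 days.
4. Report the results side by side, and say that the creatinine slope will be interpreted cautiously if they differ. Do not make agreement in direction a condition for a claim.

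The cost is SAP wording and four extra model runs (two outcomes in each of two models), on samples already scheduled, plus the matched-visit creatinine display. Cystatin C is not drawn at EVd or Visit 99, so the check stops at Week 52 and cannot test later slope data. It supplements the creatinine slope and does not replace it.

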3.14. Safety Analyses

Unless specified otherwise, safety analyses will be conducted in the safety population (Table GPID.3.1). All events that occur between the first dose date of study drug and the end date of follow-up will be included in the safety analyses, regardless of the adherence to study drug.

The statistical assessment of homogeneity of the distribution of categorical safety responses between tirzepatide MTD and placebo will be conducted using Fisher's exact test, unless specified otherwise. Risk difference and its 95% CI will also be provided, where appropriate.

The mean change from baseline differences among treatments at all scheduled visits will be assessed via an MMRM analyses using REML. Unless specified otherwise, the MMRM analysis will contain measurements from planned visits up to 104 weeks, and the model will include treatment group, stratification factors, visit and treatment-by-visit interaction as fixed effects, and baseline value of the safety parameter as a covariate. To model the covariance structure within participants, the unstructured covariance matrix will be used. If this model fails to converge, the covariance structures specified in Section 3.13.1.4 will be tested in order until convergence has been met. If the data does not warrant the MMRM model, then an ANCOVA model will be conducted.

For selected safety parameters, a time-to-first-event analysis via the Cox-proportional hazards model may be conducted. Participants without the event will be censored at the end of follow-up.

3.14.1. Analysis of Adverse Events

3.14.1.1. Treatment-Emergent Adverse Events

A treatment-emergent AE (TEAE) is defined as an event that first occurred or worsened in severity after the first dose of study treatment. The MedDRA lowest level term (LLT) will be used in the treatment-emergent derivation. The maximum severity for each LLT during the baseline period, including ongoing medical history, will be used as baseline severity. For events with a missing severity during the baseline period, the event will be treated as mild in severity for determining treatment-emergence. Events with a missing severity during the postbaseline period will be treated as severe and treatment-emergence will be determined by comparing to baseline severity.

For events occurring on the day of taking study medication for the first time, the case report form (CRF)-collected information (for example, treatment emergent flag, start time of study treatment, and event) will be used to determine whether the event was pre- versus posttreatment if available. If the relevant information is not available, then the events will be counted as posttreatment.

Unless otherwise specified, the counts and percentages of participants with TEAEs will be summarized by treatment using the MedDRA PT nested within SOC. Statistical comparisons will be applied at both the SOC and PT levels. Events will be ordered by decreasing frequency in tirzepatide arm within SOC. The SOC will be in alphabetical order. For events that are sexspecific, the denominator and computation of the percentage will include only participants from the given sex.

An overview of the number and percentage of participants who experienced a TEAE, serious AE (SAE), death, or discontinued from study treatment or study due to an AE will be summarized by treatment.

The counts and percentages of patients with TEAEs by maximum severity will be summarized by treatment using MedDRA PT within SOC. For each participant and TEAE, the maximum severity for the MedDRA PT is the maximum postbaseline severity observed from all associated LLTs mapping to the MedDRA PT. The maximum severity will be determined based on the nonmissing severities. If all severities are missing for the defined postbaseline period of interest, it will show as missing in the table.

